7.1.1. Potential Cases of Acute Kidney Injury

Participants exposed to IMP demonstrating transient or sustained increase in Screat (with decrease in Screat-based eGFR or eCrCL) require expedited evaluation to differentiate AKI from DICI. DICI is defined as transporter-mediated effect related to altered renal tubular creatinine handling without histological injury.

AKI may be due to one or more types of injury, including DIKI. Differentiation of DIKI from other causes of AKI and from DICI may require clinical, radiographic, histopathologic, and laboratory assessments, as well as nephrology consultation.

Follow-up Assessments

The participant should return to the site for evaluation as soon as possible, preferably within 48 hours of awareness of the abnormal results.

Evaluation should include physical examination, laboratory tests, detailed medical and surgical history, review of all medications (including recreational drugs and supplements [herbal]), family history, sexual history, travel history, blood transfusion, and potential occupational exposure to chemicals.

Laboratory assessments should include simultaneous serum cystatin C (Scys) and serum creatinine (Screat) tests. Estimates of eGFR, eCrCl and Screat-based eGFR and combined Screat-Scys-based eGFR should also be derived using the appropriate equation described in [Appendix 7](#).

Assessments of urine albumin-to-creatinine ratio or urine volume may also be performed as appropriate.

Differentiating Acute Kidney Injury from DICI

A confirmed Screat increase is defined as:

- (i) ≥ 0.3 mg/dL (≥ 26.5 μ mol/L) within 48 hours OR
- (ii) confirmed Screat increase ≥ 1.5 times baseline (known or suspected to have occurred within the prior 7 days).

Based on the assessments performed, suspected AKI (including DIKI) may be differentiated from DICI as follows.

Adult participants

	AKI (including DIKI) Any one of the below	DICI
Scys & Screat	Simultaneous, confirmed serum cystatin C (Scys) increase and confirmed Screat increase	Confirmed Screat increase without confirmed increase in reflex Scys AND

	AKI (including DIKI) Any one of the below	DICI
eGFR	Decrease in Screat-based eGFR and combined Screat-Scys-based eGFR (when available)	Confirmed Screat-based eGFR decrease without confirmed combined Screat-Scys-based eGFR decrease.
Albuminuria or proteinuria	Confirmed albuminuria increase (see Appendix 7 for Grades A1 to A3 quantitation)	
Urine volume	Urine volume <0.5 mL/kg/h for 6 consecutive hours	

Regardless of the presence or absence of increase in Screat, DIKI and other causes of AKI may be suspected if either there is new-onset or worsening albuminuria or proteinuria are detected.

All confirmed cases of clinically relevant decrease in kidney function should be considered potential cases of DIKI if no other reason for the kidney function abnormalities has been found.

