a. Cystatin C (Scys): Screening or Baseline Scys is recommended to help differentiate post-baseline DIKI from DICI. Post-baseline, Scys is measured if and only if serum creatinine increase post-baseline is observed (see Section 7.1.1). b. Screening, Baseline and Post-baseline (only in case of reflex measurement of Scys) eGFR is calculated using 2021 CKD-EPI eGFR (combined Screat and Scys- based) equation (see Section 10.7.2) is recommended to assess presence or absence of post-baseline change in kidney function. c. Only if UTI is suspected and urine dipstick is positive for nitrites or leukocyte esterase or both. d. For confirmation of postmenopausal status only in females <60 years old and not using hormonal or HRT only. e. The minimum requirement for drug screening includes cocaine, THC, opiates/opioids, benzodiazepines, and amphetamines (others are site- and study-specific). f. Test as reflex if HBsAg and/or HBCAb are positive.			

The investigator must review the laboratory report, document this review, and record any clinically relevant changes occurring during the study in the AE section of the CRF.

Laboratory/analyte results that could unblind the study and have been collected for the purpose of the study will not be reported to investigator sites or other blinded personnel until the study has been unblinded.

Any remaining serum/plasma from samples collected for clinical safety laboratory measurements at baseline and at all times after dose administration may be retained and stored for the duration of the study. Upon completion of the study, these retained safety samples may be used for the assessment of exploratory safety biomarkers or unexpected safety findings. These data will not be included in the CSR. Samples to be used for this purpose will be shipped to either a Pfizer-approved BBS facility or other designated laboratory and retained for up to 1 year following the completion of the study.

10.3. Appendix 3: Adverse Events: Definitions and Procedures for Recording, Evaluating, Follow-Up, and Reporting

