10.7.2. Age-Specific Kidney Function Calculation Recommendations

10.7.2.1. Adults (18 Years and Above)—2021 CKD-EPI Equations

eGFR (mL/min/1.73m²)²³

2021 CKD-EPI Screat Only	Screat (mg/dL)	Scys (mg/L)	Recommended eGFR Equation
Female	if ≤ 0.7	NA	$eGFR = 143 \times (Screat/0.7)^{-0.241} \times (0.9938)^{Age}$
Female	if > 0.7	NA	$eGFR = 143 \times (Screat/0.7)^{-1.200} \times (0.9938)^{Age}$
Male	if ≤ 0.9	NA	$eGFR = 142 \times (Screat/0.9)^{-0.302} \times (0.9938)^{Age}$
Male	if > 0.9	NA	$eGFR = 142 \times (Screat/0.9)^{-1.200} \times (0.9938)^{Age}$
2021 CKD-EPI Screat-Scys Combined	Screat (mg/dL)	Scys (mg/L)	Recommended eGFR Equation
Female	if ≤ 0.7	if ≤ 0.8	$eGFR = 130 \times (Screat/0.7)^{-0.219} \times (Scys/0.8)^{-0.323} \times (0.9961)^{Age}$
Female	if ≤ 0.7	if > 0.8	$eGFR = 130 \times (Screat/0.7)^{-0.219} \times (Scys/0.8)^{-0.778} \times (0.9961)^{Age}$
Female	if > 0.7	if ≤ 0.8	$eGFR = 130 \times (Screat/0.7)^{-0.544} \times (Scys/0.8)^{-0.323} \times (0.9961)^{Age}$
Female	if > 0.7	if > 0.8	$eGFR = 130 \times (Screat/0.7)^{-0.544} \times (Scys/0.8)^{-0.778} \times (0.9961)^{Age}$
Male	if ≤ 0.9	if ≤ 0.8	$eGFR = 135 \times (Screat/0.9)^{-0.144} \times (Scys/0.8)^{-0.323} \times (0.9961)^{Age}$
Male	if ≤ 0.9	if > 0.8	$eGFR = 135 \times (Screat/0.9)^{-0.144} \times (Scys/0.8)^{-0.778} \times (0.9961)^{Age}$
Male	if > 0.9	if ≤ 0.8	$eGFR = 135 \times (Screat/0.9)^{-0.544} \times (Scys/0.8)^{-0.323} \times (0.9961)^{Age}$
Male	if > 0.9	if > 0.8	$eGFR = 135 \times (Screat/0.9)^{-0.544} \times (Scys/0.8)^{-0.778} \times (0.9961)^{Age}$

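### The eGFR row of the AKI-versus-DICI table in Protocol 7.1.1 contradicts the table's own cystatin C row: a creatinine-only rise lowers combined eGFR and so meets the AKI column

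*Protocol*

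**What the plan says.** Protocol 7.1.1 states that "DICI is defined as transporter-mediated effect related to altered renal tubular creatinine handling without histological injury". It then gives a table for telling suspected AKI, including drug-induced kidney injury (DIKI), from DICI.

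- **AKI column.** The header is "AKI (including DIKI) Any one of the below". One row asks for simultaneous confirmed rises in serum cystatin C (Scys) and serum creatinine (Screat). The eGFR row is "Decrease in Screat-based eGFR and combined Screat-Scys-based eGFR (when available". It gives no size and does not use the word *confirmed*. Albuminuria and urine volume have their own rows.
- **DICI column.** Two conditions are joined: "Confirmed Screat increase without confirmed increase in reflex Scys AND" and "Confirmed Screat-based eGFR decrease without confirmed combined Screat-Scys-based eGFR decrease".

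The section gives sizes for a confirmed change in Screat only: at least 0.3 mg/dL within 48 hours, or "confirmed Screat increase ≥ 1.5 times baseline". Neither 7.1.1 nor Appendix 7 says how large an eGFR fall must be to count as a decrease or a confirmed decrease.

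The equations are in Protocol 10.7.2.1, under "2021 CKD-EPI Screat-Scys Combined". On baseline cystatin C, Table 5 footnote a says "Screening or Baseline Scys is recommended to help differentiate post-baseline DIKI from DICI", while 10.7.1 treats baseline Scys values as needed for the calculation.

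**The concern.** The two DICI conditions are meant to describe one pattern: creatinine moves, cystatin C does not, and true filtration is intact. The second condition uses combined eGFR as if it did not respond to creatinine, but creatinine is one of its two laboratory inputs. If a creatinine-only rise always pulls combined eGFR down, the eGFR row overrides the cystatin C row in exactly the case the table is there to separate.

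At stake is how kidney findings are labelled in a first-in-human study whose primary objective is safety. A rise that the protocol's own definition would call DICI could be evaluated and reported as suspected AKI or DIKI. Section 7.1.1 also treats confirmed, clinically relevant falls in kidney function with no other explanation as potential DIKI.

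**Working it through.** The plan states no figure to reproduce. The check applies the protocol's own equations to the protocol's own creatinine criteria.

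**Inputs (10.7.2.1).** Combined eGFR = c × (Screat/k)^a × (Scys/0.8)^b × 0.9961^Age.
- Women: c = 130, k = 0.7, a = −0.219 (Screat ≤ 0.7) or −0.544 (above).
- Men: c = 135, k = 0.9, a = −0.144 (Screat ≤ 0.9) or −0.544 (above).
- Both: b = −0.323 (Scys ≤ 0.8) or −0.778 (above).

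DICI is modelled as Screat up and Scys unchanged. This follows the table's Scys row and the definition of DICI as a creatinine-handling effect.

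**Step 1: direction.** With Scys and age fixed, multiplying Screat by r > 1 on one branch multiplies combined eGFR by r^a. Every a is negative, so the factor is below 1. The branches meet at Screat = k, so crossing from one to the other does not change the direction. Screat-based eGFR falls for the same reason.

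**Step 2: size.** For a 1.5-fold rise:
- a = −0.544: 1.5^−0.544 = 0.802, a fall of 19.8%.
- a = −0.144: 1.5^−0.144 = 0.943, a fall of 5.7%.

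Examples at age 40, Scys 0.8 mg/L:

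| Case | Screat (mg/dL) | Combined eGFR | Screat-based eGFR |
|---|---|---|---|
| Man | 0.6 to 0.9 | 122.4 to 115.5 (−5.7%) | 125.1 to 110.7 (−11.5%) |
| Man | 0.9 to 1.2 | 115.5 to 98.7 (−14.5%) | 110.7 to 78.4 (−29.2%) |
| Woman | 0.7 to 1.0 | 111.2 to 91.6 (−17.6%) | 111.5 to 72.7 (−34.8%) |
| Woman | 0.7 to 1.05 | 111.2 to 89.2 (−19.8%) | 111.5 to 68.5 (−38.5%) |

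The second row in full: 135 × 0.9961^40 = 115.5, and 115.5 × (1.2/0.9)^−0.544 = 115.5 × 0.855 = 98.7.

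A grid covered both sexes, ages 18, 40 and 65, Screat 0.40–1.40 mg/dL and Scys 0.50–1.20 mg/L, keeping baseline combined eGFR of at least 75 (the eligibility floor in 5.2). Each baseline was raised by 0.3 mg/dL and by 1.5-fold. Combined eGFR fell in 3268 of 3268 combinations, by 5.7–19.8%. The grid limits are assumptions. They affect the range but not the direction.

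**Step 3: what would cancel the fall.** Within one branch, Scys must be multiplied by r^(−a/b), which is below 1. For r = 1.5:
- a = −0.144, b = −0.778: 1.5^(−0.144/0.778) = 0.928, a 7% fall in Scys.
- a = −0.544, b = −0.323: 1.5^(−0.544/0.323) = 0.505, a fall of about 50%.

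Suppose true Scys is flat and each measurement varies by an assumed within-person CV of 3–10%. The chance that noise alone prevents a fall is then 0–5% for rises of 0.3 mg/dL from 0.7 (women) or 0.9 (men). For a man going from 0.6 to 0.9 it is 4–28%.

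**Step 4: the table applied to Screat up, Scys flat.**

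| Row | AKI column | DICI column |
|---|---|---|
| Scys and Screat | not met | met |
| eGFR, read literally | met: both eGFRs fall | not met: combined eGFR falls |

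One row suffices for AKI and both are needed for DICI, so the table returns AKI. A repeat test does not change this, because a sustained Screat rise gives a sustained fall. If combined eGFR is unavailable, the AKI row appears to rest on the Screat-based fall alone, which is also present.

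**The case against.** The strongest reply is the word *confirmed*. The DICI cell uses it and the AKI cell does not. For Screat, the same section gives it a size. If it carries a size for eGFR too, a pure creatinine rise could satisfy DICI. That is a fair reading, but no size is given. The KDIGO bands in 10.7.4 are for adverse event grading and 7.1.1 does not tie its eGFR row to them. The unthresholded AKI row would still be met, leaving the participant in both columns with no precedence rule. This changes the form of the defect without removing it.

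Other objections stand and limit the point:

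- **A reader might infer that the table can never return DICI.** It can. The DICI column rules out only a confirmed Scys rise, so a large enough measured Scys fall avoids the problem.
- **A reader might infer that every such participant will be classified as AKI.** Section 7.1.1 presents the table as a way the two may be told apart and allows for clinical, imaging and histological work-up and nephrology advice.
- **A reader might infer that the primary endpoint is misstated or a stopping rule triggered.** The SAP text supplied has no AKI, DIKI or DICI output, and laboratory values go against sponsor reporting standards (SAP 3.1.2, 6.1.2). The 50% criterion in 6.6.1 turns on clinically significant abnormalities indicating dose-limiting intolerance, not on this label. Section 7.1.1 has no automatic withdrawal, unlike 7.1.2. Any effect on escalation is indirect.
- **A reader might infer that a creatinine-only rise is expected with this drug.** Protocol 4.2 mentions possible transporter inhibition, but the names are redacted. No readable passage says that the drug acts on renal creatinine handling.

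**Conclusion.** The concern holds as a matter of internal consistency and should be fixed. For the pattern that the Scys row assigns to DICI, the eGFR row gives the opposite answer. The direction follows from the negative exponents alone. The size, about 6–20% in combined eGFR, applies to rises just at the protocol's creatinine criteria with Scys unchanged, over the assumed grid.

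The practical consequence is mislabelling of creatinine-only rises as suspected AKI or DIKI in kidney safety evaluation and adverse event reporting, subject to clinical judgement. The documents support no effect on sample size, PK analyses or planned safety tables beyond the adverse event label.

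**What to change.** Reconcile the two eGFR cells of the 7.1.1 table with the Scys row, the DICI definition and the equations in 10.7.2.1, so that a creatinine-only rise does not meet the AKI column through the creatinine term alone. In the same edit, state:

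- what counts as a decrease and as a confirmed decrease in eGFR;
- which column prevails if both are met.

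Also reconcile Table 5 footnote a, where baseline Scys is only recommended, with 10.7.1, where it is needed. Without a baseline Scys value, no change in combined eGFR can be calculated.

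The criterion and any threshold are for the sponsor to choose; none is proposed here. The cost is a text change to one table row and one footnote. Cystatin C is already listed in Table 5, so no extra visit is implied.

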7.1.2. ECG Changes

A participant who meets either bulleted criteria based on the average of triplicate ECG readings will be withdrawn from the study intervention.

- QTcF >500 ms.
- Change from baseline: QTcF >60 ms.

If a clinically significant finding is identified (including, but not limited to, changes from baseline in QTcF after enrollment), the investigator or qualified designee will determine if the participant can continue in the study and if any change in participant management is needed. This review of the ECG printed at the time of collection must be documented. Any new clinically relevant finding should be reported as an AE.

7.1.3. COVID-19

If a participant has COVID-19 during the study, this should be reported as an AE or SAE (as appropriate) and appropriate medical intervention provided. Study treatment should continue unless the investigator/treating physician is concerned about the safety of the participant, in which case temporary or permanent discontinuation may be required.

It is recommended that the investigator discuss temporary or permanent discontinuation of study intervention with the study medical monitor.

7.2. Participant Discontinuation/Withdrawal From the Study

A participant may withdraw from the study at any time at their own request. Reasons for discontinuation from the study include the following:

- Refused further study procedure;
- Lost to follow-up
- Death;
- Study terminated by sponsor;
- Discretion of the investigator or sponsor for safety or behavioral reasons, or the inability of the participant to comply with the protocol required schedule of study visits or procedures.

At the time of discontinuing from the study, if possible, an early discontinuation visit should be conducted. See the [SoA](#) for assessments to be collected at the time of study discontinuation and follow-up and for any further evaluations that need to be completed.

The early discontinuation visit applies only to participants who are enrolled/randomized and then are prematurely withdrawn from the study. Participants should be questioned regarding their reason for withdrawal.

The participant will be permanently discontinued from the study intervention and the study at that time.

If a participant withdraws from the study, they may request destruction of any remaining samples taken and not tested, and the investigator must document any such requests in the site study records and notify the sponsor accordingly.

If the participant withdraws from the study and also withdraws consent (see [Section 7.2.1](#) for disclosure of future information, no further evaluations will be performed and no additional data will be collected. The sponsor may retain and continue to use any data collected before such withdrawal of consent.

7.2.1. Withdrawal of Consent

Participants who request to discontinue receipt of study intervention will remain in the study and must continue to be followed for protocol specified- follow-up procedures. The only exception to this is when a participant specifically withdraws consent for any further contact with them or persons previously authorized by the participant to provide this information. Participants should notify the investigator in writing of the decision to withdraw consent from future follow-up, whenever possible. The withdrawal of consent should be explained in detail in the medical records by the investigator, as to whether the withdrawal is only from further receipt of study intervention or also from study procedures and/or posttreatment study follow-up-, and entered on the appropriate CRF page. In the event that vital status (whether

the participant is alive or dead) is being measured, publicly available information should be used to determine vital status only as appropriately directed in accordance with local law.

7.3. Lost to Follow-Up

A participant will be considered lost to follow-up if the participant repeatedly fails to return for scheduled visits and is unable to be contacted by the study site.

The following actions must be taken if a participant fails to return to the clinic for a required study visit:

- The site must attempt to contact the participant and reschedule the missed visit as soon as possible. Counsel the participant on the importance of maintaining the assigned visit schedule and ascertain whether the participant wishes to and/or should continue in the study;
- Before a participant is deemed lost to follow-up, the investigator or designee must make every effort to regain contact with the participant (where possible, 3 telephone calls and, if necessary, a certified letter to the participant's last known mailing address or local equivalent methods). These contact attempts should be documented in the participant's medical record;
- Should the participant continue to be unreachable, the participant will be considered to have withdrawn from the study.

8. STUDY ASSESSMENTS AND PROCEDURES

8.1. Administrative Procedures

The investigator (or an appropriate delegate at the investigator site) must obtain a signed and dated ICD before performing any study specific- procedures.

Study procedures and their timing are summarized in the [SoA](#). Protocol waivers or exemptions are not allowed.

Adherence to the study design requirements, including those specified in the [SoA](#), is essential and required for study conduct.

All screening evaluations must be completed and reviewed to confirm that potential participants meet all eligibility criteria. The investigator will maintain a screening log to record details of all participants screened and to confirm eligibility or record reasons for screening failure, as applicable.

Participants will be screened within 28 days prior to administration of the study intervention to confirm that they meet the study population criteria for the study. If the time between screening and dosing exceeds 28 days as a result of unexpected delays (eg, delayed drug shipment), then participants do not require rescreening if the laboratory results obtained prior to first dose administration meet eligibility criteria.

A participant who qualified for this protocol but did not enroll from an earlier cohort/group may be used in a subsequent cohort/group without rescreening, provided laboratory results obtained prior to the first dose administration meet eligibility criteria for this study. In addition, other clinical assessments or specimen collections, eg, retained research samples, may not need to be repeated, as appropriate.

Every effort should be made to ensure that protocol required- tests and procedures are completed as described. However, it is anticipated that from time to time there may be circumstances outside the control of the investigator that make it unfeasible to perform the test. In these cases, the investigator must take all steps necessary to ensure the safety and well-being of the participant. When a protocol required- test cannot be performed, the investigator will document the reason for the missed test and any corrective and preventive actions that they have taken to ensure that required processes are adhered to as soon as possible. The study team must be informed of these incidents in a timely manner.

Safety, laboratory, or analyte results that have been collected for the purposes of this study and could unblind the study will not be reported to investigative sites or other blinded personnel until the study has been unblinded.

If an IV catheter is utilized for blood sample collections, ECGs and vital sign assessments (pulse rate and BP) should be collected prior to the insertion of the catheter.

For samples being collected and shipped, detailed collection, processing, storage, and shipment instructions and contact information will be provided to the investigator site prior to initiation of the study.

The total blood sampling volume for individual participants in this study is approximately 480 mL. The actual collection times of blood sampling may change. Additional blood samples may be taken for safety assessments at times specified by Pfizer, provided the total volume taken during the study does not exceed 550 mL during any period of 56 consecutive days.

To prepare for study participation, participants will be instructed on the information in the [Lifestyle Considerations](#) and [Concomitant Therapy](#) sections of the protocol.

8.2. Efficacy Assessments

Efficacy parameters are not evaluated in this study.

8.3. Safety Assessments

Planned time points for all safety assessments are provided in the [SoA](#). Unscheduled safety measurements may be obtained at any time during the study to assess any perceived safety issues.

8.3.1. Physical Examinations

Physical examinations are to be performed at the nominal timepoints specified in the [SoA](#). Additional physical examinations will be permitted, as necessary, to ensure appropriate collection of safety data.

A complete physical examination will include, at a minimum, head, ears, eyes, nose, mouth, skin, heart and lung examinations, lymph nodes, and gastrointestinal, musculoskeletal, and neurological systems.

A brief physical examination will include, at a minimum, assessments of general appearance, the respiratory and cardiovascular systems, and participant-reported symptoms.

Physical examinations may be conducted by a physician, trained physician's assistant, or nurse practitioner as acceptable according to local regulation.

Height and weight will also be measured and recorded as per the [SoA](#). For measuring weight, a scale with appropriate range and resolution is used and must be placed on a stable, flat surface. Participants must remove shoes, bulky layers of clothing, and jackets so that only light clothing remains. They must also remove the contents of their pockets and remain still during measurement of weight.

Physical examination findings collected during the study will be considered source record and will not be required to be reported, unless otherwise noted. Any untoward physical examination findings that are identified during the active collection period and meet the definition of an AE or SAE ([Appendix 3](#)) must be reported according to the processes in [Sections 8.4.1 to 8.4.3](#).

